9.5 Inducement

Subjects will be reimbursed for their transport to attend all visits to the health centre.

9.6 Community

Prior to study commencement, the health facilities catchment areas (Shehia) will be gathered together through their local leaders (Sheha). In these meetings investigators will brief the community leaders about the study and stress the importance of completion of the entire follow-up schedule of 28 days. They will be invited to ask questions and full explanation will be provided to any raised issue. A copy of the study consent form will be provided to each Sheha to enable any community member to read more about the study.

10. BUDGET TEMPLATE

. professional scientific staff 3pple*300,000/- per month*12 months . technical staff 40pple*100,000/- per month*12 months . technical staff 40pple*100,000/- per month*12 months . local support 20pple*50,000/- per ltr lst phase . l	Human resources		Tsh	USD				
technical staff 40pple*100,000/- per month*12 months local support 20pple*50,000/- per month*12 months local support 20pple*50,000/- per month*12 months Sub-total 70 800 000,00 8 275,86 Sub-total 70 800 000,00 48 827,59 Transport for Local supervision 24 visits*25lts*1,650/- per ltr 1st phase 11 980 000,00 8 193,10 360 visits*25lts*1,650/- per ltr 2nd phase 360 visits*25lts*1,650/- per ltr 3rd phase Sub-total 43 560 000,00 20 482,76 Sub-total 43 560 000,00 30 041,38 Equipment and supplies equipment (thermometers, lab equips ets) supplies (slides, cotton, spirit, lancets, giemsa etc) supplies (slides, cotton, spirit, lancets, giemsa etc) sub-total 28 600 000,00 7 724,14 - operational costs (space rental, communication) Sub-total Contingency fees for clinical trials ethical review 450 000,00 310,34 Patient incentive costs (bus fares for follow up and free LLIN) Patients bus fares (100pts*1,000per trip*9trips) 2,250 000,00 310,34 Patient incentive costs (bus fares for follow up and free LLIN) Patients bus fares (100pts*1,000per trip*9trips) 2,250 000,00 310,34 Patienting support for research institutions, capacity building Sub-total 29 50 000,00 17 241,38 Sub-total 20 000,00 18 241,38 Supervision Local Supervisors 3 120 000,00 2 151,72 Quality assurance system (data validation, slides cross-check) Sub-total Sub-total 2 300 000,00 5 014,14 Laboratory support	* · · · · · · · · · · · · · · · · · · ·	nth*12	10 000 000 00	7 440 20				
local support 20pple*50,000/- per month*12 months 12 000 000,00 48 827,59		.l	,					
Sub-total 70 800 000,00			, and the second					
Transport for Local supervision	· local support 20pple*50,000/- per month*12 months		·					
24 visits*25lts*1,650/- per ltr 1st phase 1 980 000,00 1 365,52 144 visits*25lts*1,650/- per ltr 2nd phase 11 880 000,00 8 193,10 360 visits*25lts*1,650/- per ltr 3rd phase 29 700 000,00 20 482,76 Sub-total 43 560 000,00 30 041,38 Equipment and supplies • equipment (thermometers, lab equips ets) 8 900 000,00 6 137,93 • supplies (slides, cotton, spirit, lancets, giemsa etc) 11 200 000,00 7 724,14 • operational costs (space rental, communication) 8 500 000,00 5 862,07 Sub-total Contingency fees for clinical trials • ethical review 450 000,00 310,34 Patient incentive costs (bus fares for follow up and free LLIN) Patients bus fares (100pts*1,000per trip*9trips) 2,250 000,00 1,551.52 Free LLINs (7,000/- pet net*100 nets) 2 250 000,00 20,332.8 Technical assistance Training for 20 Lab technicians 25 000 000,00 17 241,38 (training, support for research institutions, capacity building) 1 450 000,00 1 1 000,00 Sub-total 3 120		Sub-total	70 800 000,00	48 827,59				
144 visits*25lts*1,650/- per ltr 2nd phase 11 880 000,00 8 193,10 360 visits*25lts*1,650/- per ltr 3rd phase 29 700 000,00 20 482,76 Sub-total 43 560 000,00 30 041,38 Equipment and supplies equipment (thermometers, lab equips ets) 8 900 000,00 7 724,14 supplies (slides, cotton, spirit, lancets, giemsa etc) 11 200 000,00 5 862,07 Contingency fees for clinical trials ethical review 450 000,00 310,34 Patient incentive costs (bus fares for follow up and free LLIN) Patient incentive costs (bus fares for follow up and free LLIN) Patient sus fares (100pts*1,000per trip*9trips) 2,250 000,00 1,551.52 Free LLINs (7,000/- pet net*100 nets) 700 000,00 482,76 Sub-total 2 500 000,00 1,7 241,38 Technical assistance Training for 20 Lab technicians 25 000 000,00 17 241,38 (training, support for research institutions, capacity building) 1 450 000,00 12 151,72 Sub-total 3 120 000,00 2 151,72 <td <="" colspan="4" td="">									360 visits*25lts*1,650/- per ltr 3rd phase 29 700 000,00 30 041,38			ŕ	•				
Sub-total 43 560 000,00 30 041,38	•		ŕ					
Equipment and supplies Supplies Supplies (slides, cotton, spirit, lancets, giemsa etc) 11 200 000,00 7 724,14 120 000,00 5 862,07 12 000 000 5 862,07 12 000 000 5 862,07 12 00 000,00 19 724,14 12 00 000,00 19 724,14 12 00 000,00 19 724,14 12 00 000,00 19 724,14 12 00 000,00 19 724,14 12 00 000,00 19 724,14 12 00 000,00 19 724,14 12 00 000,00 19 724,14 12 00 000,00 19 724,14 12 00 000,00 19 724,14 12 00 000,00 19 724,14 12 00 000,00 10 0	360 visits*25lts*1,650/- per ltr 3rd phase		29 700 000,00	20 482,76				
• equipment (thermometers, lab equips ets) 8 900 000,00 6 137,93 • supplies (slides, cotton, spirit, lancets, giemsa etc) 11 200 000,00 7 724,14 • operational costs (space rental, communication) 8 500 000,00 5 862,07 Sub-total 28 600 000,00 19 724,14 Contingency fees for clinical trials • ethical review 450 000,00 310,34 Patients lous fares for follow up and free LLIN) Patients bus fares (100pts*1,000per trip*9trips) 2,250 000,00 1,551.52 Free LLINs (7,000/- pet net*100 nets) 700 000,00 482,76 Sub-total 2 950 000,00 2,033,28 Technical assistance Training for 20 Lab technicians 2 5 000 000,00 17 241,38 (training, support for research institutions, capacity building) 1 450 000,00 1 000,00 Sub-total 2 6 450 000,00 2 151,72 Quality assurance system (data validation, slides cross-check) 3 120 000,00 1 586,21 Data management (data entry, data analysis,		Sub-total	43 560 000,00	30 041,38				
Supplies (slides, cotton, spirit, lancets, giemsa etc)	Equipment and supplies							
• operational costs (space rental, communication) 8 500 000,00 5 862,07 Sub-total 28 600 000,00 19 724,14 Contingency fees for clinical trials 450 000,00 310,34 • ethical review 450 000,00 310,34 Patient incentive costs (bus fares for follow up and free LLIN) Patients bus fares (100pts*1,000per trip*9trips) 2,250 000,00 1,551.52 Free LLINs (7,000/- pet net*100 nets) 700 000,00 482,76 Sub-total 2 950 000,00 2,033.28 Technical assistance 25 000 000,00 17 241,38 (training, support for research institutions, capacity building) 1 450 000,00 1 000,00 Sub-total 26 450 000,00 18 241,38 Supervision 3 120 000,00 2 151,72 Quality assurance system 3 120 000,00 2 151,72 Quality assurance system Sub-total 2 300 000,00 1 586,21 Data management Gual analysis, report writing) 5 014,14 Laboratory support	· equipment (thermometers, lab equips ets)		8 900 000,00	6 137,93				
Sub-total 28 600 000,00 19 724,14	· supplies (slides, cotton, spirit, lancets, giemsa etc)		11 200 000,00	7 724,14				
Contingency fees for clinical trials • ethical review 450 000,00 310,34 Sub-total 450 000,00 310,34 Patients review costs (bus fares for follow up and free LLIN) Patients bus fares (100pts*1,000per trip*9trips) 2,250 000,00 1,551.52 Free LLINs (7,000/- pet net*100 nets) 700 000,00 482,76 Sub-total 2 950 000,00 2,033.28 Technical assistance Training for 20 Lab technicians 25 000 000,00 17 241,38 (training, support for research institutions, capacity building) 1 450 000,00 1 000,00 Sub-total 26 450 000,00 18 241,38 Supervision Local Supervisors 3 120 000,00 2 151,72 Quality assurance system (data validation, slides cross-check) Sub-total 2 300 000,00 1 586,21 Data management (data entry, data analysis, report writing) 5 014,14 Laboratory support	· operational costs (space rental, communication)		8 500 000,00	5 862,07				
• ethical review 450 000,00 310,34 Sub-total 450 000,00 310,34 Patient incentive costs (bus fares for follow up and free LLIN) Patients bus fares (100pts*1,000per trip*9trips) 2,250 000,00 1,551.52 Free LLINs (7,000/- pet net*100 nets) 700 000,00 482,76 Sub-total 2 950 000,00 2,033.28 Technical assistance Training for 20 Lab technicians 25 000 000,00 17 241,38 (training, support for research institutions, capacity building) 1 450 000,00 1 000,00 Sub-total 26 450 000,00 18 241,38 Supervision Local Supervisors 3 120 000,00 2 151,72 Quality assurance system (data validation, slides cross-check) Sub-total 2 300 000,00 1 586,21 Data management (data entry, data analysis, report writing) 5 014,14 Laboratory support		Sub-total	28 600 000,00	19 724,14				
Sub-total 450 000,00 310,34	Contingency fees for clinical trials							
Sub-total 450 000,00 310,34	· ethical review		450 000,00	310,34				
Patient incentive costs (bus fares for follow up and free LLIN) Patients bus fares (100pts*1,000per trip*9trips) 2,250 000,00 1,551.52 Free LLINs (7,000/- pet net*100 nets) 700 000,00 482,76 Sub-total 2 950 000,00 2,033.28 Technical assistance Training for 20 Lab technicians 25 000 000,00 17 241,38 (training, support for research institutions, capacity building) 1 450 000,00 1 000,00 Sub-total 26 450 000,00 18 241,38 Supervision Local Supervisors 3 120 000,00 2 151,72 Quality assurance system (data validation, slides cross-check) Sub-total 2 300 000,00 1 586,21 Data management (data entry, data analysis, report writing) 5 014,14 Laboratory support		Sub-total	450 000,00	·				
Tree LLINs (7,000/- pet net*100 nets) 700 000,00 482,76	Patient incentive costs (bus fares for follow up and free LLI	N)						
Sub-total 2 950 000,00 2,033.28 Technical assistance Training for 20 Lab technicians 25 000 000,00 17 241,38 (training, support for research institutions, capacity building) 1 450 000,00 1 000,00 Sub-total 26 450 000,00 18 241,38 Supervision Sub-total 3 120 000,00 2 151,72 Quality assurance system Quality assurance system Sub-total 2 300 000,00 1 586,21 Data management (data entry, data analysis, report writing) Sub-total 7 270 500,00 5 014,14 Laboratory support Laboratory support	Patients bus fares (100pts*1,000per trip*9trips)		2,250 000,00	1,551.52				
Technical assistance Training for 20 Lab technicians (training, support for research institutions, capacity building) 25 000 000,00 17 241,38 Supervision Sub-total 26 450 000,00 18 241,38 Supervision 3 120 000,00 2 151,72 Sub-total 3 120 000,00 2 151,72 Quality assurance system (data validation, slides cross-check) Sub-total 2 300 000,00 1 586,21 Data management (data entry, data analysis, report writing) Sub-total 7 270 500,00 5 014,14 Laboratory support Laboratory support	Free LLINs (7,000/- pet net*100 nets)		700 000,00	482,76				
Training for 20 Lab technicians (training, support for research institutions, capacity building) 25 000 000,00 17 241,38 Sub-total 26 450 000,00 1 000,00 Supervision Local Supervisors 3 120 000,00 2 151,72 Sub-total 3 120 000,00 2 151,72 Quality assurance system (data validation, slides cross-check) Sub-total 2 300 000,00 1 586,21 Data management (data entry, data analysis, report writing) Sub-total 7 270 500,00 5 014,14 Laboratory support		Sub-total	2 950 000,00	2,033.28				
(training, support for research institutions, capacity building) 1 450 000,00 1 000,00 Sub-total 26 450 000,00 18 241,38 Supervision 3 120 000,00 2 151,72 Local Supervisors 3 120 000,00 2 151,72 Sub-total 3 120 000,00 2 151,72 Quality assurance system (data validation, slides cross-check) Sub-total 2 300 000,00 1 586,21 Data management (data entry, data analysis, report writing) 5 014,14 Laboratory support Sub-total 7 270 500,00 5 014,14	Technical assistance							
capacity building) 1 450 000,00 1 000,00 Sub-total 26 450 000,00 18 241,38 Supervision 3 120 000,00 2 151,72 Sub-total 3 120 000,00 2 151,72 Quality assurance system Company of the	Training for 20 Lab technicians		25 000 000,00	17 241,38				
Sub-total 26 450 000,00 18 241,38	(training, support for research institutions,							
Supervision Local Supervisors 3 120 000,00 2 151,72 Sub-total 3 120 000,00 2 151,72 Quality assurance system (data validation, slides cross-check) 2 300 000,00 1 586,21 Data management (data entry, data analysis, report writing) 5 014,14 Laboratory support 5 014,14	capacity building)		1 450 000,00	1 000,00				
Local Supervisors 3 120 000,00 2 151,72		Sub-total	26 450 000,00	18 241,38				
Sub-total 3 120 000,00 2 151,72 Quality assurance system (data validation, slides cross-check) Sub-total 2 300 000,00 1 586,21 Data management (data entry, data analysis, report writing) 5 014,14 Laboratory support 5 014,14	Supervision							
Quality assurance system (data validation, slides cross-check) Sub-total 2 300 000,00 1 586,21 Data management (data entry, data analysis, report writing) Sub-total 7 270 500,00 5 014,14 Laboratory support	Local Supervisors		3 120 000,00	2 151,72				
(data validation, slides cross-check) Sub-total 2 300 000,00 1 586,21 Data management (data entry, data analysis, report writing) Sub-total 7 270 500,00 5 014,14 Laboratory support Sub-total 7 270 500,00 5 014,14		Sub-total	3 120 000,00	2 151,72				
(data validation, slides cross-check) Sub-total 2 300 000,00 1 586,21 Data management (data entry, data analysis, report writing) Sub-total 7 270 500,00 5 014,14 Laboratory support Sub-total 7 270 500,00 5 014,14	Quality assurance system							
Sub-total 2 300 000,00 1 586,21 Data management (data entry, data analysis, report writing) Sub-total 7 270 500,00 5 014,14 Laboratory support Sub-total 7 270 500,00 5 014,14								
Data management (data entry, data analysis, report writing) Sub-total 7 270 500,00 5 014,14 Laboratory support		Sub-total	2 300 000,00	1 586,21				
(data entry, data analysis, report writing) Sub-total 7 270 500,00 5 014,14 Laboratory support	Data management		,	/				
Sub-total 7 270 500,00 5 014,14 Laboratory support								
Laboratory support		Sub-total	7 270 500.00	5 014.14				
	Laboratory support		. = . 0 000,00					
	(genotyping)							

Su	ıb-total	0	-
Miscellaneous			
Su	b-total	2 500 000,00	1 724,14
GRAND TOTAL		186,200,500	128,414

Appendix 1. DEFINITION OF SEVERE FALCIPARUM MALARIA1

Severe manifestation of *P. falciparum* malaria in adults and children

Clinical manifestations

- prostration,
- impaired consciousness,
- respiratory distress (metabolic acidosis),
- multiple convulsions,
- circulatory collapse,
- pulmonary oedema (radiological),
- abnormal bleeding,
- jaundice,
- haemoglobinurea.

Laboratory findings

- severe anaemia (haemoglobin < 5 g/dl, haematocrit < 15%),
- hypoglycaemia (blood glucose < 2.2 mmol/l or 40 mg/dl),
- acidosis (plasma bicarbonate < 15 mmol/l),
- hyperlactataemia (venous lactic acid > 5 mmol/l),
- hyperparasitaemia (> 4% in non-immune patients),
- renal impairment (serum creatinine above normal range for age).

Classification of severe malaria in children

Group 1: children at increased risk for death

- prostration
- respiratory distress

Group 2: children at risk for clinical deterioration

- haemoglobin < 5 g/dl, haematocrit < 15%
- two or more convulsions within 24 h

Group 3: children with persistent vomiting

¹ World Health Organization. Severe falciparum malaria. *Transactions of the Royal Society of Tropical Medicine and Hygiene*, 2000, 94(Suppl. 1):1–90.

Appendix 2. MEDICATIONS (WITH ANTIMALARIAL ACTIVITY) THAT SHOULD NOT BE USED **DURING THE STUDY PERIOD**

- chloroquine, amodiaquine;
- quinine, quinidine;
- mefloquine, halofantrine, lumefantrine;
- artemisinin and its derivatives (artemether, arteether, artesunate, dihydroartemisinin);
- proguanil, chlorproguanil, pyrimethamine;
- sulfadoxine, sulfalene, sulfamethoxazole, dapsone;
- primaquine;
- atovaquone;
- antibiotics: tetracycline*, doxycycline, erythromycin, azythromycin, clindamycin, rifampicin, trimethoprim;
- pentamidine.

^{*} Tetracycline eye ointments can be used.

Appendix 3. DOSING CHART OF ARTESUNATE + AMODIAQUINE AND PRIMAQUINE

A fixed dose combination of artesunate + amodiaquine (Artesunate Amodiaquine Winthrop®, Sanofi Aventis), prequalified by the WHO, will be used as study drug. Tablets containing 25/67.5 mg, 50/135mg and 100/270 mg, base of artesunate/amodiaquine will be administered according to the dosing chart below:

Body	Number of tablets of Artesunate (AS) + Amodiaquine (AQ)								
weight	Day 0	Day 1	Day 2						
<10 kg	1 tab	1 tab	1 tab						
	(AS 25 mg + AQ 67.5 mg)	(AS 25 mg + AQ 67.5 mg)	(AS 25 mg + AQ 67.5 mg)						
10-20 kg	1 tab	1 tab	1 tab						
	(AS 50 mg + AQ 135 mg)	(AS 50 mg + AQ 135 mg)	(AS 50 mg + AQ 135 mg)						
21-30 kg	2 tab	2 tab	2 tab						
	(AS 50 mg + AQ 135 mg)	(AS 50 mg + AQ 135 mg)	(AS 50 mg + AQ 135 mg)						
>30 kg	2 tab	2 tab	2 tab						
	(AS 100 mg + AQ 270 mg)	(AS 100 mg + AQ 270 mg)	(AS 100 mg + AQ 270 mg)						

	DOSAGE AND ADMINISTRATION OF PRIMAQUINE								
	WEIGHT AGE Single low dose [o hrs]								
1	5-9 kg	1-4 yrs	2.5 mg						
2	10-20 kg	5-8 yrs	5 mg						
3	20-40 kg	9-14 yrs	10 mg						
4	>40 kg	15+ yrs	15 mg						

Pediatric dosing of SLD primaquine:

To dissolve tablets in Water:

- a. Based on patients weight dissolve one tablet(s) (15mg) of Primaquine in 5 ml of
- b. Ensure that the solution is thoroughly mixed.
- c. Measure the volume (cc) of solution to give to the participant based on the participant's weight. The drug will be mixed with equal volume of juice to mask its bitter test

Picture 1: Sanofi product, Primaquine phosphate USP Tablets 26.3 mg (15 mg equivalent base)

The extemporaneous preparation should be conducted as follows

- the extemporaneous preparation should be conducted as follows:

 Define number of 15mg (primaquine base) tablets required based on patient's age or weight.

 Crush tablets in mortar with pestle.

 Pour powder into the clean container to be used for dilution (preferably glass container as there is no data on interaction with plastic).

 Based on 15 ml. of water for 1 tablet, measure in a graduated syringe the required volume of water needed to dissolve the tablets. Use a fraction of water from the syringe to rinse the mortar and pestle, and pour contents into the container.

 In the container, mix the powder and fiquid thoroughly with a spoon.

 Leave for 1 minute to rest. Some residuals (exceptients not dissolved such as tale) will appear on the bottom of the container and do not need to be withdrawn.

 Based on patient's weight, withdraw required volume with graduated syringe, avoiding the exception at the bottom of the container. See table 1 below for examples.

 The prepared solution can be stored in the glass container for a maximum of 3 days at 40°C or 7 days at 30°C, protected from light.

 Do not store the prepared solution inside the syringe as there are no data available on potential interactions between syringe materials and primaquine.

Age (years)	ears) Weight (kg) Dosage (mg) (0.25 x weight)		Volume to be withdrawn (ml) (for a solution of 1mg/ ml)	Syringes recommended for administration		
1	9	2.25	2.25	5 ml		
6	18	4.5	4.5	10 ml		
14	36	9.0	9.0	10 ml (or 20 ml)		

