3.5 Inclusion criteria

- Age 3 months and above;
- P. falciparum infection detected by mRDT and confirmed by microscopy;
- presence of *P. falciparum* malaria asexual parasitaemia (any level);
- presence of axillary \geq 37.5 °C or history of fever during the past 48 hours
- ability to swallow oral medication;
- ability and willingness to comply with the study protocol for the duration of the study and to comply with the study visit schedule; and
- informed consent from the patient or from a parent or guardian in the case of children.

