4. TREATMENT

4.1 Antimalarial treatment

Artesuate + amodiaquine will be administered orally as a fixed dose combination, i.e. Artesunate/Amodiaquine Winthrop®, prequalified by the WHO, at a dose of approximately artesunate 4 mg/kg + amodiaquine 10mg/kg once daily for 3 consecutive days.

Primaquine will be administered orally, i.e. ®, prequalified by the WHO, as a single dose (0.25 mg/kg) together with the first artesunate + amodiaquine dose of approximately artesunate 4 mg/kg + amodiaquine 10mg/kg once daily for 3 consecutive days.

The study drugs, represent the present drugs deployed to public health care facilities by the Zanzibar Ministry of Health.

The investigators will be instructed to record the batch number and expiry date of the test medicines. The correct drug dosages will be determined from the dosing charts (Appendix 3), which are in accordance with the national treatment guidelines in Zanzibar.

All doses of medicine will be administered under direct supervision of a qualified member of the staff designated by the principal investigator. The study patients will be observed for 30 minutes after medicine administration for adverse reactions or vomiting. Any patient who vomits during this observation period will be re-treated with the same dose of medicine and observed for an additional 30 minutes. If the patient vomits again after the second study drug administration, he/she will be withdrawn and offered rescue therapy (see below section 4.3 Rescue treatment).

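### Appendix 3 gives two strengths for the paediatric primaquine solution, with volumes for only one, and places a recorded 20 kg in two dose rows

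*Combined protocol and SAP*

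**What the plan says.** Section 4.1 sets primaquine at 0.25 mg/kg, given once with the first artesunate + amodiaquine (AS+AQ) dose. It then states: "The correct drug dosages will be determined from the dosing charts (Appendix 3", and describes these as charts "which are in accordance with the national treatment guidelines in Zanzibar". Appendix 3 is therefore the operative dosing instruction.

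On primaquine, Appendix 3 contains:

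- **A dose chart** with four weight rows: 5-9 kg (2.5 mg), 10-20 kg (5 mg), 20-40 kg (10 mg) and above 40 kg (15 mg). The parallel age column runs 1-4, 5-8, 9-14 and 15 or more years.
- **A first preparation method for children.** Step a: "Based on patients weight dissolve one tablet(s) (15mg) of Primaquine in 5 ml of" (the line stops there in the available text). Step c: "Measure the volume (cc) of solution to give to the participant based on" the child's weight. No volumes are listed with this method.
- **A second, extemporaneous method**: "Based on 15 ml. of water for 1 tablet, measure in a graduated syringe the required volume". It leads to a table ("See table 1 below for examples") whose volume column is headed "for a solution of 1mg/ ml" and whose doses are 0.25 x weight.

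The AS+AQ chart in the same appendix uses non-overlapping bands (10-20 kg, then 21-30 kg), and its lowest band is everything under 10 kg. Section 3.5 admits patients of "Age 3 months and above" and sets no minimum weight. Section 5.2.2 has weight recorded to the nearest kilogram.

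**The concern.** A nurse or clinician who follows Appendix 3 as printed meets two instructions that cannot both hold.

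First, the same tablet is made up at two strengths, and nothing says which method applies to whom. Both methods ask for a volume chosen by weight, but the only volumes in the appendix belong to one strength.

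Second, a child recorded at 20 kg can be given either of two doses that differ by a factor of two.

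The patients affected are children, and the Objectives name haematological adverse events of primaquine as something the study will evaluate. Haemoglobin is measured on days 0, 3, 7, 14 and 28 for that purpose. Reading those results requires knowing what dose each child received.

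**Working it through.** **Inputs.** Target dose 0.25 mg/kg (section 4.1). Tablet 15 mg base; water volumes 5 ml and 15 ml; chart rows; example volumes of 2.25, 4.5 and 9.0 ml at 9, 18 and 36 kg (all Appendix 3). Weight to the nearest kilogram (section 5.2.2).

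**1. Reproduce the printed volumes.** Volume = 0.25 x weight / concentration.

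- 15 ml method: 15 mg / 15 ml = 1 mg/ml. Volumes are 0.25 x 9 / 1 = 2.25 ml, 0.25 x 18 / 1 = 4.5 ml and 0.25 x 36 / 1 = 9.0 ml. All three match the table.
- 5 ml method: 15 mg / 5 ml = 3 mg/ml. The same doses would need 0.75, 1.5 and 3.0 ml. These are not printed.

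So the table fits the 15 ml method only. Step c of the first method also adds juice, but only after the volume has been measured. The juice does not change the dose or reconcile the two strengths.

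**2. Dose if the printed volumes were drawn from the 5 ml solution.**

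- 9 kg: 2.25 ml x 3 mg/ml = 6.75 mg; 6.75 / 9 = 0.75 mg/kg.
- 18 kg: 4.5 ml x 3 mg/ml = 13.5 mg; 13.5 / 18 = 0.75 mg/kg.
- Ratio to target: 0.75 / 0.25 = 3.
- Upper weight, assuming one tablet is dissolved: 5 ml / 0.25 ml per kg = 20 kg. At 36 kg the printed 9 ml exceeds the 5 ml available.

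**3. The 20 kg overlap.**

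- Row 10-20 kg: 5 / 20 = 0.25 mg/kg. Row 20-40 kg: 10 / 20 = 0.50 mg/kg.
- With rounding to the nearest kilogram, a recorded 20 kg covers true weights of about 19.5 to 20.5 kg.
- The highest mg/kg where the chart is unambiguous: 2.5 / 5 = 0.50 at 5 kg; 5 / 10 = 0.50 at 10 kg; 10 / 21 = 0.48 at 21 kg. The higher reading at 20 kg is inside the chart's own range.

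**4. Below 5 kg.** There is no weight row, and the age column starts at 1 year. The 0.25 mg/kg rule would give 0.25 x 4 = 1 mg at 4 kg. Using the lowest row instead would give 2.5 / 4 = 0.63 mg/kg.

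**The case against.** The case for leaving Appendix 3 alone has four parts.

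*The 5 ml line is damaged text.* It breaks off mid-sentence, in a part of the appendix that reads poorly, so a character or a clause may have been lost. This stands as a limit on certainty: the line may be a slip for 15 ml, or the source page may read differently. But the figure of 5 ml is legible and conflicts with 15 ml, so the source page needs checking.

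*The threefold dose is hypothetical.* This stands. Staff would have to make the 5 ml solution and then use a table labelled for 1 mg/ml. A reader might infer that the protocol prescribes a threefold overdose. It does not; it leaves the only printed volumes beside a preparation they do not fit.

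*There are tie-breakers at 20 kg.* The 0.25 mg/kg target gives exactly 5 mg, and the chart has an age column. Neither settles it. Section 4.1 names the chart as the dose source, and the chart departs from 0.25 mg/kg through most of its bands. The age column can point to either row, depending on whether the child falls in the 5-8 or the 9-14 year group. What does stand is that 0.50 mg/kg is no more than the chart gives at 5 and 10 kg, so it should not be read as an out-of-range dose.

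*The under-5 kg item is a gap, not a contradiction.* This also stands. The 0.25 mg/kg rule could fill it, severe malnutrition is an exclusion, and the documents do not show that any such infant would be enrolled.

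A reader might also count the chart against the example table: 2.5 v 2.25 mg at 9 kg, 5 v 4.5 mg at 18 kg, 10 v 9 mg at 36 kg. The chart is 11% higher each time (for example 2.5 / 2.25 = 1.11). The table is offered as examples, and the difference lies well within ordinary weight banding. It is not an error.

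**Conclusion.** Two internal conflicts in the paediatric primaquine instructions hold: two strengths (3 v 1 mg/ml) with volumes for only one, and a recorded 20 kg in two rows (5 or 10 mg). The 20 kg overlap is plain on the text. The dilution conflict is less certain because its line is incomplete.

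The 0.75 mg/kg figure assumes that staff mix the two methods, that one tablet is dissolved, and that the 5 ml figure is as printed. It applies only up to 20 kg. The absent row below 5 kg is a secondary gap.

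The number of children affected cannot be estimated, because the documents give no weight distribution. Nothing here bears on the PCR-corrected failure rate or the sample size, and a reader should not infer that the efficacy results are compromised. The point concerns clear dosing of children and interpretable haematological safety data. It is worth correcting because section 4.1 makes this appendix binding and the remedy is nearly free.

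**What to change.** Before enrolment, amend Appendix 3:

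1. Keep one preparation, 15 ml per tablet (1 mg/ml), which the printed volumes already fit. Check the 5 ml line against its source, then delete or correct it.
2. Start the third primaquine row at 21 kg, so that a recorded 20 kg gets 5 mg. This follows the AS+AQ chart's split at 20/21 kg. Section 4.1 says the charts follow national guidelines, which are not reproduced in the protocol, so check the change against them first.
3. While the chart is open, state the dose below 5 kg (0.25 mg/kg) or state that primaquine is omitted.

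Optionally, and not as a correction, add a field to the day 0 case report form for the mg or ml of primaquine given. The form records tablets, which does not describe a measured volume.

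The cost is a text correction and, if wanted, one form field. No extra patients, visits or procedures are needed.
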